4.1 Inclusion criteria

Patients eligible for inclusion in this study must fulfill all of the following criteria:

- 1. Patient must be able to understand and communicate with the investigator and comply with the requirements of the study and must provide written, signed and dated informed consent before any study assessment is performed.
- 2. Male or non-pregnant, non-lactating female patients at least 18 years of age.
- 3. PsA patients must fulfill the following criteria:
 - Diagnosis of PsA classified by CASPAR criteria with symptoms for at least 6 months (Appendix 3) and
 - Active PsA as assessed by ≥ 1 tender joints out of 78 and ≥ 1 swollen joints out of 76 at Baseline (dactylitis of a digit counts as 1 joint each).
- 4. AxSpA patients must fulfill the following criteria:
 - AxSpA as per the classification of the ASAS axial SpA criteria (Appendix 4) with objective signs of inflammation at screening, evident by either MRI with Sacroiliac joint inflammation or definite radiographic sacroilitis according to the modified New York criteria (Appendix 5) (both according to source documentation) and/or hsCRP > ULN (as defined by central lab) and
 - Active disease assessed by total BASDAI \geq 4 (0-10) (Appendix 6) at Baseline.
- 5. Diagnosis of Achilles tendon enthesitis according to swelling and tenderness at the insertional site of the Achilles tendon into the calcaneus.
- 6. Onset of heel pain ≥ 1 month at Baseline.
- 7. Heel enthesitis that is MRI-positive according to the investigator's judgement.
- 8. The heel enthesitis must have been refractory to standard treatment defined as either NSAIDs for at least 1 month at the maximal recommended or tolerated dose unless withdrawal because of intolerance, toxicity or contraindications or TNF-inhibitors as described in inclusion criterion 16.
- 9. Rheumatoid factor (RF) and anti-cyclic citrullinated peptide (anti-CCP) antibodies negative at Screening.
- 10. Patients should have been on NSAIDs at the highest recommended dose for at least 1 month prior to randomization with an inadequate response or failure to respond, or less if

therapy had to be withdrawn due to intolerance, toxicity or contraindications or on TNF-inhibitors as described in inclusion criterion 16.

- 11. Patients who are regularly taking NSAIDs as part of their PsA or axSpA therapy are required to be on a stable dose for at least 2 weeks before study randomization and should remain on a stable dose up to Week 24.

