4.2 Exclusion criteria

Patients fulfilling any of the following criteria are not eligible for inclusion in this study. No additional exclusions may be applied by the investigator, in order to ensure that the study population will be representative of all eligible patients.

- 1. Chest X-ray or chest MRI with evidence of ongoing infectious or malignant process obtained within 3 months prior to screening and evaluated by a qualified physician.
- 2. Patients taking high potency opioid analgesics (e.g. methadone, hydromorphone, morphine).
- 3. Previous exposure to secukinumab or other biologic drug directly targeting IL-17 or IL-17 receptor.
- 4. Use of any investigational drug and/or devices within 4 weeks before randomization or a period of 5 half-lives of the investigational drug, whichever is longer.
- 5. Ongoing use of psoriasis treatments / medications (e.g. topical corticosteroids, UV therapy) at randomization. The following wash out periods need to be observed:

- Oral or topical retinoids: 4 weeks.
- Photochemotherapy (e.g. PUVA): 4 weeks.
- Phototherapy (UVA or UVB): 2 weeks.
- Topical skin treatments (except in face, eyes, scalp and genital area during screening, only corticosteroids with mild to moderate potency): 2 weeks.
- 6. History of hypersensitivity to any of the study drugs or its excipients or to drugs of similar chemical classes.
- 7. Any intramuscular or intravenous corticosteroid treatment within 4 weeks before randomization.
- 8. Any therapy by intra-articular injections (e.g. corticosteroid) within 4 weeks before randomization.
- 9. Patients who have previously been exposed to more than two (2) TNF inhibitors (investigational or approved).
- 10. Patients who have ever received biologic immunomodulating agents, except those targeting $TNF\alpha$.
- 11. Previous treatment with any cell-depleting therapies including but not limited to anti-CD20, investigational agents (e.g. Campath, anti-CD4, anti-CD5, anti-CD3, anti-CD19).
- 12. Pregnant or nursing (lactating) women, where pregnancy is defined as the state of a female after conception and until the termination of gestation, confirmed by a positive human chorionic gonadotropin (hCG) laboratory test.

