### **2.3.1 Patient disposition**

The number and percentage of patients who are screened will be presented. In addition, the reasons for screen failures will be provided.

The number and percentage of patients who are enrolled, and who completed each treatment period and who discontinued the study will be summarized by treatment group at the end of each treatment period. In addition, for those patients who discontinued, the summary will be broken down by primary reason for study discontinuation.

The number and percentage of patients who took the rescue medication and hence discontinued at week 24 will be presented. For each protocol deviation (PD), the number and percentage of patients for whom the PD applies will be tabulated.

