#### **5.5 Rule of exclusion criteria of analysis sets**

##### **Table 5.1-4 Protocol deviations that cause subjects to be excluded**

Deviation ID	Description of Deviation	Exclusion in Analyses	Severity code
INCL01A	ICF is not signed or missing or date of signing ICF is missing	EXCLUDE FROM FAS AND SAF	3
INCL01B	ICF date is after visit or assessment date	INCLUDE IN EVERYTHING	0
INCL02A	Pregnant or lactating female patients	INCLUDE IN EVERYTHING	0
INCL02B	Age is less than 18 years	INCLUDE IN EVERYTHING	0
INCL03A	Diagnosis of PsA classified by CASPAR criteria with no symptoms or symptoms for less than 6 months	INCLUDE IN EVERYTHING	0
INCL03B	Active PsA as not assessed by greater than 1/78 tender joints and greater than 1/76 swollen joints at Baseline.	INCLUDE IN EVERYTHING	0
INCL04A	No objective signs of inflammation at Screening, no evident of Sacroiliac joint inflammation or radiographic sacroilitis and hsCRP less than ULN	INCLUDE IN EVERYTHING	0
INCL04B	Total BASDAI < 4 (0–10) at Baseline	INCLUDE IN EVERYTHING	0
INCL05	Subject with no diagnosis of Achilles tendon enthesitis	INCLUDE IN EVERYTHING	0
INCL06	Onset of heel pain < 1 month or > 5 years at baseline	INCLUDE IN EVERYTHING	0
INCL07	Heel enthesitis is not MRI-positive according to the investigator's judgement.	INCLUDE IN EVERYTHING	0
INCL08	Subject is intolerable or toxified or contraindicated to NSAIDs standard treatment for heel enthesitis	INCLUDE IN EVERYTHING	0
INCL09	Rheumatoid factor (RF) or anti-cyclic citrullinated peptide (anti-CCP) antibodies is positive at Screening	INCLUDE IN EVERYTHING	0
INCL10A	Subject are inadequate response to NSAIDs at the highest recommended dose at least 1 month prior to randomization to enroll into study.	INCLUDE IN EVERYTHING	0
INCL10B	Subject is inadequate response or failure to respond, or less than 1 month if therapy	INCLUDE IN EVERYTHING	0
INCL11A	Subject is unstable to remain on regular dose of NSAIDs as part of PsA or axSpA therapy for 2 weeks before study randomization	INCLUDE IN EVERYTHING	0
INCL11B	Subject is unable to remain up to Week 24 on stable regular dose of NSAIDs as part of PsA or axSpA therapy	INCLUDE IN EVERYTHING	0
INCL12A	Patient taking corticosteroid is unable to remain on stable dose of less than or equal of 10 mg/day prednisone for 2 weeks before randomization	INCLUDE IN EVERYTHING	0
INCL12B	Patient taking corticosteroid is unable to remain on stable dose up to week 24	INCLUDE IN EVERYTHING	0

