INCL13A	Patient taking MTX or axSpA-sulfasalazine is not taken it for atleast 3 months	INCLUDE IN EVERYTHING	0
INCL13B	Patient taking MTX or axSpA-sulfasalazine is unable to remain on stable dose for at least 4 weeks prior to randomization	INCLUDE IN EVERYTHING	0
INCL13C	Patient taking MTX or axSpA-sulfasalazine is unable	INCLUDE IN	0

Deviation ID	Description of Deviation	Exclusion in Analyses	Severity code
	to remain on stable dose for up to Week 24	EVERYTHING	
INCL14	Patient is on MTX but not on folic acid supplementation at randomization	INCLUDE IN EVERYTHING	0
INCL15A	Patient who is on DMARD other than MTX or - only in case of axSpA - sulfasalazine is not discontinued the DMARD for 4 weeks prior to randomization.	INCLUDE IN EVERYTHING	0
INCL15B	Patients who are on leflunomide, has not been discontinued for 8 weeks unless a cholestyramine washout has been performed prior to randomization to randomized into study.	INCLUDE IN EVERYTHING	0
INCL16	Patients are not TNF $\alpha$ inhibitor-naïve	INCLUDE IN EVERYTHING	0
EXCL01	Chest X-ray or chest MRI with evidence of ongoing infectious or malignant process	INCLUDE IN EVERYTHING	0
EXCL02	Patient took high potency opioid analgesics (e.g. methadone, hydromorphone, morphine).	INCLUDE IN EVERYTHING	0
EXCL03	Previous exposure to secukinumab or other biologic drug directly targeting IL-17 or IL-17 receptor	INCLUDE IN EVERYTHING	0
EXCL04	Patient used any of investigational drug and/or devices within 4 weeks before randomization or a period of 5 half-lives of the investigational drug.	INCLUDE IN EVERYTHING	0
EXCL05A	Patient is using Oral or topical retinoids of psoriasis treatments / medications	INCLUDE IN EVERYTHING	0
EXCL05B	Patient is using Phototherapy of psoriasis treatments / medications and not undergone 4 weeks of washout treatment	INCLUDE IN EVERYTHING	0
EXCL05C	Patient is using Phototherapy of psoriasis treatments / medications and not undergone 2 weeks of washout treatment	INCLUDE IN EVERYTHING	0
EXCL05D	Patient is using Topical skin treatments of psoriasis treatments / medications and not undergone 2 weeks of washout treatment	INCLUDE IN EVERYTHING	0
EXCL06	History of hypersensitivity to any of the study drugs or its excipients or to drugs of similar chemical classes	INCLUDE IN EVERYTHING	0
EXCL07	Any intramuscular or intravenous corticosteroid treatment within 4 weeks before randomization	INCLUDE IN EVERYTHING	0

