EXCL08	Any therapy by intra-articular injections (e.g. corticosteroid) within 4 weeks before randomization.	INCLUDE IN EVERYTHING	0
EXCL09	Patients previously have been treated with TNF inhibitors	INCLUDE IN EVERYTHING	0
EXCL10	Patients have received biologic immunomodulating agents	INCLUDE IN EVERYTHING	0
EXCL11	Previous treatment with any cell-depleting therapies including but not limited to anti-CD20, investigational agents	INCLUDE IN EVERYTHING	0
EXCL12	Pregnant or nursing (lactating) women, confirmed by a positive human chorionic gonadotropin (hCG) laboratory test	INCLUDE IN EVERYTHING	0
EXCL13	Women of childbearing potential, defined as all women physiologically capable of becoming pregnant, unless they are using effective methods of contraception before 3 months during dosing of study treatment	INCLUDE IN EVERYTHING	0
EXCL14	Active ongoing inflammatory diseases or including	INCLUDE IN	0

Deviation ID	Description of Deviation	Exclusion in Analyses	Severity code
	inflammatory bowel disease or uveitis.	EVERYTHING	
EXCL15	Patient unacceptable risk for participation in the opinion of the investigator for underlying metabolic, hematologic, renal, hepatic, pulmonary, neurologic, endocrine, cardiac, infectious or gastrointestinal conditions in the opinion of the investigator	INCLUDE IN EVERYTHING	0
EXCL16	Significant medical problems or diseases, including but not limited to the following: uncontrolled hypertension or congestive heart failure or uncontrolled diabetes.	INCLUDE IN EVERYTHING	0
EXCL17A	Any single parameter (AST/SGOT, ALT/SGPT, alkaline phosphatase) exceeded 2 × ULN.	INCLUDE IN EVERYTHING	0
EXCL17B	Total bilirubin concentration is increased above 2 × ULN and serum bilirubin exceeding the value of 1.6 mg/dL (27 µmol/L).	INCLUDE IN EVERYTHING	0
EXCL18	History of renal trauma, glomerulonephritis, or patients with 1 kidney only, or a serum creatinine level exceeding 1.5 mg per dL	INCLUDE IN EVERYTHING	0
EXCL19	Screening total white blood cell (WBC) count less than 3000/µL, or platelets less than 100000/µL or neutrophils less than 1,500/µL or hemoglobin less than 8.5 g per dL (85 g per L).	INCLUDE IN EVERYTHING	0
EXCL20	Active systemic infections during the last 2 weeks (exception: common cold) prior to randomization.	INCLUDE IN EVERYTHING	0
EXCL21	Patient is having history of ongoing, chronic or recurrent infectious disease or evidence of tuberculosis infection	INCLUDE IN EVERYTHING	0

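### Five rows of the SAP's deviation list flag patients whom the current protocol admits, so the planned deviation table would report eligible patients as entry violators

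*SAP*

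**What the plan says.** SAP 2.3.1 commits to a count per deviation: "For each protocol deviation (PD), the number and percentage of patients for whom the PD applies will be tabulated". The SAP's only list of deviations is Table 5.1-4, which gives each an identifier, a description and a population code.

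- **TNF exposure.** INCL16 flags patients who are not TNFα "inhibitor-naïve". EXCL09 reads "Patients previously have been treated with TNF inhibitors". EXCL10 flags receipt of biologic immunomodulating agents without qualification. Protocol 4.1, criteria 16 and 17, admits patients who have had up to two TNF inhibitors, given inadequate response or intolerance and a completed washout. Protocol 4.2, exclusion 9, bars "Patients who have previously been exposed to more than two (2) TNF inhibitors (investigational or approved", and exclusion 10 exempts agents that target TNFα.
- **Heel pain.** INCL06 reads "Onset of heel pain < 1 month or > 5 years at baseline". Protocol criterion 6 reads "Onset of heel pain ≥ 1 month at Baseline" and has no upper limit.
- **Joint counts (PsA).** INCL03B is worded around more than 1 tender and more than 1 swollen joint. Protocol criterion 3 asks for at least 1 of each.
- **NSAID history.** INCL08 reads "Subject is intolerable or toxified or contraindicated to NSAIDs standard treatment for heel enthesitis" and INCL10A reads "Subject are inadequate response to NSAIDs at the highest recommended dose at least 1 month prior to randomization to enroll into study". Protocol criteria 8 and 10 require NSAID failure. They also accept withdrawal for intolerance, toxicity or contraindication, or the TNF-inhibitor route.

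All these rows carry population code 0, which keeps the patient in every analysis set. SAP section 4 declares no change from the protocol.

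**The concern.** A deviation list should flag patients who break the criteria in force. Here several rows state a different criterion, and the patients affected are ones the protocol means to study. Protocol 1.2 names disease active despite anti-TNF therapy. Section 9.4.2 puts TNFα inhibitor status in the primary model, and section 9.5.1.6 makes it a preplanned subgroup. The study report could therefore analyse a group as eligible and, in the disposition section, count the same patients as entry violators.

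There is also a loss in the other direction. When one row catches both eligible and ineligible TNF-exposed patients, its count no longer shows how many real breaches of the TNF criteria occurred. What is at stake is how accurately the report describes trial conduct and eligibility, not the treatment comparison.

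**Working it through.** The plan states no figure to reproduce here. The check is a comparison of texts, followed by a bound on the number of patients.

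**Step 1. Rows against criteria.**

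| SAP row | Flags | Current protocol | Eligible patient wrongly flagged |
|---|---|---|---|
| INCL16 | not TNF-naive | inclusions 16-17 admit up to two TNF inhibitors | one or two inhibitors, inadequate response or intolerance, washed out |
| EXCL09 | any prior TNF inhibitor | exclusion 9: more than two | the same patient |
| EXCL10 | any biologic immunomodulator | exclusion 10 exempts TNFα agents | the same patient |
| INCL06 | onset under 1 month or over 5 years | inclusion 6: at least 1 month | heel pain over 5 years |
| INCL03B | not more than 1 tender and more than 1 swollen joint | inclusion 3: at least 1 of each | PsA with exactly one tender or one swollen joint |

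EXCL10 does reach TNF inhibitors: the footnote to protocol Table 5-1 classes them as biologic immunomodulators.

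**Step 2. Can true TNF violations be separated?** Take three patients:
- A had one inhibitor with an inadequate response (eligible).
- B had three inhibitors (ineligible).
- C had one inhibitor with neither inadequate response nor intolerance (ineligible).

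Read as written, INCL16, EXCL09 and EXCL10 flag all three in the same way. B and C are captured, but nothing distinguishes them from A.

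**Step 3. Effect on analysis sets.** SAP Table 5.1-5 removes patients from the FAS for codes 1 and 3 and from the safety set for codes 2, 3 and 6. The rows in Step 1 are all code 0. Patients removed: none.

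**Step 4. Size on TNF status.** About 200 patients are to be randomized (protocol 3.1), with no more than 40% TNF-IR (protocol 3.1 and 5.3). The protocol glossary counts intolerance as inadequate response, so the ceiling covers both routes in criterion 16.

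- Upper bound: 0.40 × 200 = 80.
- Lower bound: 0, because no minimum is set.

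**Step 5. Adding heel pain (illustration only).** The documents give no share with heel pain over 5 years. Assume a share h of 0 to 30%, independent of the TNF-exposed share t. The share with at least one false flag is 1 − (1 − t)(1 − h).

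| t | h = 0 | h = 10% | h = 30% |
|---|---|---|---|
| 0 | 0 | 10% (20) | 30% (60) |
| 20% | 20% (40) | 28% (56) | 44% (88) |
| 40% | 40% (80) | 46% (92) | 58% (116) |

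Figures in brackets are patients out of 200. INCL03B could add some PsA patients, who are planned as about half of the total (0.50 × 200 = 100). No share with exactly one joint is given.

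**The case against.** The strongest reply is that nothing inferential depends on this table. Its stated purpose is to map deviations to population codes, and SAP 2.3.1 does not cite it by name. That much is right. But it is the only deviation list in the SAP, so it is the natural source for the promised counts, and protocol section 11 sends significant deviations to the study report.

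A second reply is that the descriptions are shorthand keyed to numbered criteria. EXCL14 omits the exception for PsA and axSpA, and EXCL21 omits the allowance after work-up of a positive tuberculosis test; nobody would code those literally. This carries weight for INCL08 and INCL10A. A reader might infer from INCL10A that every patient who qualified by NSAID failure becomes a violator, but the row is a badly worded label, and the documents do not show that it or INCL08 reflects an outdated rule. EXCL10 and INCL03B may also be loose drafting, although as worded they catch eligible patients. The reply fails for INCL16, EXCL09 and INCL06, which state different rules and not abbreviated ones.

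A third reply is that the SAP, with a single version dated 23 June 2016 and an 8-week screening period, was probably not updated for Amendment 3. That explains the mismatch without curing it.

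Finally, prior therapies are summarised elsewhere (SAP 2.3.2 and 2.4.2), so the report would still describe who was studied. That limits the harm.

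**Conclusion.** The mismatch is real and worth correcting, with consequences limited to deviation reporting. Followed as written, the SAP would count eligible patients as entry violators: 0 to about 80 of 200 on TNF status, plus an unknown number for heel pain duration and joint count. It would also leave real TNF breaches indistinguishable from eligible exposure. This assumes that the counts in SAP 2.3.1 are drawn from Table 5.1-4 as worded, and that patients entered under the current criteria.

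Three stronger conclusions are tempting and not supported:
- The table's title speaks of deviations that cause exclusion, so a reader might infer that TNF-exposed patients leave the FAS. Code 0 rules that out.
- A reader might infer that most of the population is affected, or multiply 80 patients by three rows to get 240 false entries. The 40% is a ceiling, the other shares are not given, and the SAP counts patients per deviation, not summed codes.
- A reader might infer that TNF violators escape the list. INCL16 and EXCL09 do catch them without separating them, and COMD01 covers washouts not observed, with the TNF washouts listed in protocol Table 5-1.

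**What to change.** Before the Week 24 lock, align Table 5.1-4 with the current protocol text:

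- **INCL16:** TNF-exposed without inadequate response or intolerance.
- **EXCL09:** more than two TNF inhibitors.
- **EXCL10:** biologic immunomodulators other than those targeting TNFα.
- **INCL06:** onset under 1 month.
- **INCL03B:** fewer than 1 tender or fewer than 1 swollen joint.
- **INCL08 and INCL10A/B:** state failure to meet the criterion, with its intolerance, toxicity, contraindication and TNF-inhibitor alternatives.

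A separate row for TNF washout is optional, since COMD01 already covers it. Assess each patient against the protocol version in force at enrolment, and keep version-specific codes if anyone entered under earlier criteria; otherwise a breach of those criteria would have no code.

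The cost is rewording the table and updating the deviation programming. Patients, analysis sets and estimates are not affected.

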- 12. Patients taking corticosteroids must be on a stable dose of ≤ 10 mg/day prednisone or equivalent for at least 2 weeks before randomization and should remain on a stable dose up to Week 24.
- 13. Patients taking MTX (7.5 mg/week to 25 mg/week) or only in case of axSpA sulfasalazine (≤ 3 g/day) are allowed to continue their medication and must have taken it for at least 3 months and have to be on a stable dose for at least 4 weeks prior to randomization and should remain on a stable dose up to Week 24.
- 14. Patients on MTX must be on folic acid supplementation at randomization.
- 15. Patients who are on a DMARD other than MTX or only in case of axSpA sulfasalazine must discontinue the DMARD 4 weeks prior to randomization, except for leflunomide, which has to be discontinued for 8 weeks prior to randomization unless a cholestyramine washout has been performed.
- 16. Patients who have been on a TNFα inhibitor (not more than two) must have experienced an inadequate response to previous or current treatment given at an approved dose for at least 3 months prior to randomization or have been intolerant to at least one administration of an anti-TNFα agent
- 17. Patients who have previously been on a TNFα inhibitor will be allowed entry into study after an appropriate wash-out period prior to randomization:
 - 4 weeks for etanercept with a terminal half-life of 102 ± 30 hours (s.c. route)
 - 8 weeks for infliximab with a terminal half-life of 8.0-9.5 days (i.v. infusion)
 - 10 weeks for adalimumab with a terminal half-life of 10-20 days (average 2 weeks) (s.c. route)
 - 10 weeks for Simponi[®] (golimumab) with a terminal half-life of 11-14 days
 - 10 weeks for Cimzia® (certolizumab) with a terminal half-life of 14 days

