Abbreviations: COX = cyclo-oxygenase, DMARD = disease modifying anti-rheumatic drug, MTX = methotrexate, NSAIDs = non-steroidal anti-inflammatory drugs, PRN = pro re nata (as needed); PUVA = psoralen and ultraviolet A; UVA = ultraviolet A; UVB = ultraviolet B: TNF = tumor necrosis factor. * These agents fall under the category of biologic immunomodulators and are prohibited medications. Administration of these agents requires study treatment discontinuation (see Section 5.6.2). ** See details about corticosteroid management in Section 5.5.7.

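### Five eligibility rows of SAP Table 5.1-4 do not match the current protocol, so eligible patients, mainly those with prior TNF inhibitors, would be reported as deviators; no analysis set changes

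*SAP*

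**What the plan says.** **Protocol.** Section 4.1, inclusion 16, accepts patients who have been on one or two TNF-alpha inhibitors, provided that they responded inadequately or were intolerant. Under inclusion 17 such patients "will be allowed entry into study after an appropriate wash-out period prior to randomization". Section 4.2, exclusion 9, removes only "Patients who have previously been exposed to more than two (2) TNF inhibitors". Exclusion 10 removes "Patients who have ever received biologic immunomodulating agents, except those targeting" TNF-alpha. Sections 3.1 and 5.3 plan for no more than 40% TNF-IR patients among about 200 randomised. Inclusion 6 sets a minimum of 1 month since onset of heel pain and no maximum. Inclusion 3 asks PsA patients for at least 1 tender and at least 1 swollen joint.

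**SAP.** Table 5.1-4 in Section 5.5 lists these deviations:

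- INCL16: "Patients are not TNF $\alpha$ inhibitor-naïve"
- EXCL09: "Patients previously have been treated with TNF inhibitors"
- EXCL10: "Patients have received biologic immunomodulating agents"
- INCL06: heel pain for under 1 month or over 5 years
- INCL03B: PsA not shown by more than 1 tender and more than 1 swollen joint

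Each row is marked for inclusion in everything, code 0. SAP 2.3.1 commits to a count and percentage of patients for every protocol deviation. SAP Section 4 records no change from the protocol's analyses.

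**The concern.** Three rows describe a trial restricted to TNF-naive patients, which the current protocol does not require. Two more apply limits that are stricter than the protocol's. If the deviation tables are programmed from this list, two errors follow.

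First, patients who met every criterion would be reported as having entered in breach of eligibility. With TNF-IR enrolment planned at up to 40%, that could be a large and misleading line in the study report.

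Second, real breaches would be hidden among permitted cases. A patient with three prior TNF inhibitors would sit in the same EXCL09 row as patients with one or two. A patient exposed without inadequate response or intolerance would sit in INCL16 beside those who qualify. Those rows could not show whether the TNF criteria were respected.

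**Working it through.** The plan states no figure to reproduce here. The check compares the SAP rows with the current eligibility text, then looks at what each code does, then sizes the effect.

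**1. Row against criterion**

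- INCL16 flags every patient who is not TNF-naive. Inclusion 16 admits up to two TNF inhibitors after inadequate response or intolerance. This is a contradiction.
- EXCL09 flags any prior TNF inhibitor. Exclusion 9 applies only above two. This is a contradiction.
- EXCL10 flags any biologic immunomodulating agent. Exclusion 10 exempts those targeting TNF-alpha. The footnote to protocol Table 5-1 says of the starred agents, which include the named TNF inhibitors, that "These agents fall under the category of biologic immunomodulators and are prohibited medications". Read literally, EXCL10 therefore catches permitted TNF-inhibitor use as well.
- INCL06 flags onset more than 5 years ago. Inclusion 6 has no upper limit. This is a contradiction.
- INCL03B treats exactly 1 tender or exactly 1 swollen joint as a failure. Inclusion 3 accepts it. This is a contradiction at the boundary.

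Nothing else in the SAP overrides these rows or ties them to a protocol version. The SAP's document history has one entry, dated 23 June 2016. A table written before Amendment 3 opened the trial to TNF-exposed patients would look like this, but that explanation is an inference.

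**2. Effect on the analysis sets**

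SAP Table 5.1-5 removes patients from the FAS on codes 1 and 3, and from the safety set on codes 2, 3 and 6. All five rows are code 0. Patients removed from either set by these rows: 0.

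**3. Size of the reporting error**

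- TNF rows. Inputs: a 40% cap and about 200 randomised (protocol 3.1 and 5.3). Ceiling = 0.40 x 200 = 80 patients.
- The protocol glossary counts intolerance as inadequate response, so the cap covers every patient who is eligible through inclusion 16.
- The same patients would appear in each TNF row, so the ceiling stays at 80 and is not multiplied by the number of rows.
- The actual share is not given. Assuming 10%: 0.10 x 200 = 20 patients. Assuming 20%: 0.20 x 200 = 40 patients.
- INCL03B. About 50% of 200 are planned to have PsA: 0.50 x 200 = 100. The share with exactly 1 tender or exactly 1 swollen joint is not given. Assuming 5%, 10% or 20%, the row would flag 5, 10 or 20 eligible patients.
- INCL06. The documents give no basis for a count.

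**The case against.** The strongest reply is that Section 5.5 exists to define the analysis sets, and for these rows it does so correctly. SAP 2.3.1 speaks of deviations that apply to a patient and does not cite Table 5.1-4. A patient who meets inclusion 16 has not deviated, and protocol 8.3 has relevant deviations determined before lock. Mass mis-listing would require someone to program the row labels in preference to the protocol. This has weight: the link is an inference. But no other deviation list is supplied, and the rows carry the identifiers that a programmer would use, so the wording should be right.

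It is also fair to say that true breaches are hidden only within these rows. SAP 2.3.2 and 2.4.2 summarise previous therapies, and 2.4.2 gives reasons for stopping psoriatic arthritis treatments. That softens the second error; it does not correct the deviation table.

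Several stronger readings are tempting, and the documents do not support them:

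- **TNF-exposed patients drop out of the analysis.** The title of Table 5.1-4 speaks of deviations that exclude subjects, so a reader might infer this. Code 0 rules it out.
- **EXCL10 is as clear a contradiction as the other two TNF rows.** TNF inhibitors have their own row in EXCL09, so EXCL10 can be read as covering other biologics. It fails only on a literal reading.
- **INCL08, INCL10A and INCL10B set rival eligibility rules.** They omit the TNF-inhibitor route in inclusions 8 and 10, and they name NSAID intolerance or inadequate response as if it were the fault. INCL10B is also an unfinished sentence. These are garbled labels, not workable alternative rules.
- **Missed TNF wash-out goes unrecorded.** There is no row for inclusion 17, but the general row COMD01 covers a wash-out that was not observed.
- **The SAP prescribes a different dose.** SAP 1.1 gives two syringes only to PsA patients with moderate-to-severe psoriasis, whereas protocol 5.2 adds TNF-exposed PsA patients. The SAP sentence is descriptive and drives no stated analysis.

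**Conclusion.** The mismatch is real. INCL16, EXCL09, INCL06 and INCL03B contradict the current protocol, and EXCL10 does so when read literally. Applied as written, they give wrong deviation counts, with a planning ceiling of 80 TNF-exposed patients (40% of those randomised) and an unknown actual number. The smaller figures for TNF exposure and for INCL03B rest on assumed percentages. The conclusion assumes that Table 5.1-4 is the list used for the tabulation in SAP 2.3.1, which is likely but not stated.

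The consequence stops at deviation reporting. The FAS, the safety set, the primary test and its power are unchanged, so this is a minor correction.

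**What to change.** In SAP Table 5.1-4, reword five codes:

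- INCL16: TNF-inhibitor exposure without inadequate response or intolerance.
- EXCL09: more than two TNF inhibitors.
- EXCL10: biologic immunomodulating agents other than those targeting TNF-alpha.
- INCL06: onset of heel pain under 1 month before Baseline.
- INCL03B: fewer than 1 tender or fewer than 1 swollen joint.

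Add one sentence stating that each code is judged against the protocol version in force at the patient's randomisation. Without it, the new wording would erase genuine breaches of the stricter criteria that applied before Amendment 3.

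The cost is small but is more than a text edit. The sponsor must supply the earlier criteria, because the previous joint-count threshold is not in these documents, and the amendment approval dates to set against randomisation dates. No protocol amendment, patients or procedures are needed. If the database is already locked, SAP Section 1 calls for an addendum.

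Three further edits are optional. Matching INCL08, INCL10A and INCL10B to inclusions 8 and 10 is copy-editing. A dedicated TNF wash-out code would largely duplicate COMD01. Aligning the dose wording in SAP 1.1 with protocol 5.2 is a separate editorial point.
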